### 3.0 Intervention to be studied

The stimulation system, custom developed at the MUSC Brain Stimulation Laboratory, consists of a commercially available, FDA-cleared (K172381) Digitimer DS7A constant current stimulator (Digitimer Ltd., USA) used with custom-built electrodes built by [name] in MUSC's Brain Stimulation Lab. This is a safe, non-invasive, and easily implemented stimulation technique which does not require MD oversight. TaVNS modulates afferent projections via stimulation of the vagus nerve through the human ear (Badran et al., 2018a) and early work shows promise for treatment of psychiatric conditions linked to overactive sympathetic responses (Badran et al., 2018c). Studies have recently demonstrated some efficacy for taVNS for reduction in symptoms of depression, including RNT, sleep disturbances and anxiety.

However, mechanisms, parameters, and the neurobiological effects are not well established (Badran et al. 2018b). Researchers on this study are experts in the development, application, and clinical use of brain stimulation techniques, and in particular are pioneers in the development and investigation of taVNS technology and its application for psychiatric treatments.

Using conductive gel, an electrode is applied and pulsed electrical stimulation is delivered at a tolerable intensity for at least half an hour, thus, stimulating the auricular branch of the vagus nerve (ABVN). The active condition will be direct electrical stimulation delivered to the inner side of the left tragus (anode in the ear canal, cathode on the surface of the tragus) based on [name] and [name] prior work. The left earlobe, used as control, has minimal ABVN innervation. The control stimulation condition will utilize identical stimulation parameters as the active condition.

Stimulation parameters will consist of 500  $\mu$ s pulse width and 10 Hz frequency. Stimulation current will be delivered at 200% of each participant's individual perceptual threshold (PT) and repeated for each stimulation condition (tragus and earlobe). PT procedure entails single pulses of stimulation to the target area and obtaining verbal confirmation of stimulation perception while modulating the current intensity via parametric estimation by sequential testing (PEST) method. This allows for determination of the minimum current intensity perceived by the participant at a specific target location.

Participants will be randomized to one of 9 dose durations with 5 participants per dose, increasing in 10 minute increments of active stimulation, ranging between 10 and 90 minutes of stimulation. All active sessions per dose will be delivered contiguously and at the end of the stimulation period, and sham stimulation at the beginning. This is to ensure that all participants have the same lapse of time between pre- and post-stimulation recording. That is, if a participant is randomized to 60 minutes of active stimulation, the first 30 minutes would be sham stimulation. After establishing the optimal dose-duration a sample of treatment seeking individuals will be recruited. This dose will be administered to individuals with anxiety and trauma symptoms to ensure that effects are sustained and to determine feasibility and tolerability.

An additional group of individuals with implanted VNS also will be evaluated after 30 minutes of stimulation. Patients at MUSC who participated in the Microtransponder Vivistim trial or other research/treatments involving VNS will be recruited to complete similar cognitive and affective tasks while psychophysiological responses are measured across 3 sessions: control (no stimulation), implanted VNS, and noninvasive taVNS. This will serve as a comparator for whether taVNS is activating similar brain and physiological regions as invasive forms of vagus nerve stimulation. This will also indicate whether mechanisms of taVNS and VNS are comparable. In order to truly determine comparability of these two forms of VNS, it is imperative to assess within subject brain, body, cognitive, and emotional responding across both implanted and non-invasive VNS.

## 4.0 Study Endpoints

The following indices will be measured to assess modulation of resting and cognitive/emotional challenge via taVNS dose. Each will be processed and scored according to published guidelines (Blumenthal et al., 2005; Boucsein et al., 2012; Gatchel et al., 1973; Keil et al., 2014). Biopac equipment will be used to continuously measure **heart rate/ variability (HRV)** and **skin conductance (SC)** to assess autonomic responses. SC increases are indicative of a sympathetically mediated orienting response (Dawson et al., 2011; Bradley, 2009). Previous studies evaluating taVNS have employed the SC within the context of fear extinction, but have not demonstrated an effect (Burger et al., 2016; 2017), though faster rates of extinction were shown. HR deceleration also is indicative of the orienting response, while higher HR variability is indicative of regulated emotional responding (Appelhans & Luecken, 2006; Bradley, 2009). Decelerations in HR after taVNS have been demonstrated under certain parameters (Badran et al., 2018b). **Pupillometry**

will be assessed to determine anxious arousal and defensive responding as a function of taVNS. Pupil dilation will be measured with a Tobii eyetracker. Previous data has shown that taVNS modulates pupil dilation. Thus, this will be used to aid in determining the optimal dose duration of taVNS.

EEG will be measured using a 32-channel BrainVision actiCHamp system. Data will be processed with BrainVision Analyzer software. Resting EEG will be measured pre-, post-, and concurrently with stimulation, and will be explored for taVNS dose dependent modulation in frequency bands and coherence of the **EEG power spectrum**. For data collected during the learning/attention task, multiple **event-related potentials** (ERPs) and **steady-state visually evoked potentials** (ssVEPs) will be assessed. A variety of ERPs indicative of attention (i.e., orienting, discrimination) will be evaluated across a variety of contexts after stimulation, including fear learning and extinction, and learning more broadly. Some studies have shown taVNS linked enhancements in the P300, an orienting response (Warren et al., 2020), whereas other studies have not (Warran et al., 2019; Keute et al., 2019). A recent evaluation found taVNS related ERP modulations indicative of enhanced cognitive control (i.e., N2; Pihlaja et al., 2020), which is typically increased during engagement of attention and is enhanced during cognitive conflict. Enhancements in the N2 are typically seen across internalizing disorders, and our previous work demonstrates that the N2 is modulated under internal and external threat (Taylor et al., 2020; Moran, Taylor, & Moser, 2012; White, Grant, Taylor et al., 2018). In addition, ssVEPs which are collected by flickering visual stimuli, may be assessed during stimulation. These potentials are modulated by attentional and motivational factors and will provide real-time dose-dependent data regarding taVNS related modulations in attention. Given the extant and emerging literature on the effects of taVNS on brain activity, these ERPs and other relevant ERPs will be explored.

Participants will complete subjective measures of anxiety and depression and related difficulties as well as Self-Reported Units of Distress (SUDs) during stimulation and the tasks and acceptability/tolerability measures (see Section 10.0 Study Design/Methods for surveys and other measures).

The above measures will also be assessed for participants with implanted invasive VNS and then subsequently with noninvasive taVNS.

## 5.0 Inclusion and Exclusion Criteria/ Study Population

This study seeks to recruit from a broad range of individuals ensure generalizability, though some exclusion criteria are necessary to ensure participant safety. Participants will call the lab and complete a phone screener which assesses for the following criteria. The recruited sample will be 50% female evenly counterbalanced across active stimulation duration and sham conditions. No racial or ethnic groups will be excluded during recruitment, nor will any other individuals with diverse backgrounds. However, participants must be English speaking, as the study consent and other tasks are presented in the English language. Risks of taVNS to a fetus are currently unknown. Thus, individuals identifying as having childbearing potential will be screened for pregnancy during the phone screener and will be provided a pregnancy test prior to stimulation to confirm they are not pregnant.

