In order to develop therapeutic taVNS for psychiatric problems, a necessary first step is to establish the appropriate parameters that will modulate cognitive and affective responses among healthy participants. We will first recruit 45 healthy participants (randomized to 9 different dose durations) to determine the dose-response curve for taVNS on a range of vagally-mediated physiological measures and subjective mood. At a single session, heart rate variability (HRV), skin conductance (SC), and electroencephalography (EEG) will be measured at baseline, concurrently with stimulation, during learning and cognitive tasks and finally during a recovery period. Utilizing rest, learning and recovery conditions concurrent with multiple physiological measures we will demonstrate whether there is process- or physiological modality-specific modulation or co-activation across domains and measures. Our team of experts in brain stimulation, neuroscience, and psychophysiology are uniquely suited to accomplish these tasks. After establishing the dose-response curve, the findings of our dosing may be evaluated an additional sample of 45 participants seeking treatment for anxiety or trauma related disorder.

An additional goal of this study is to evaluate invasive vagus nerve stimulation (VNS) to determine how taVNS relates to other established forms of brain stimulation via the vagus nerve. VNS is currently FDA approved for depression and epilepsy, and research has indicated that patients also report decreased anxiety symptoms. Therefore, patients with previously implanted VNS, will be invited to complete this study. They will be administered similar tasks as participants who receive taVNS, and a full psychophysiological profile will be assessed. This study will only recruit individuals who currently have implanted VNS, given the invasive procedure. Although VNS is FDA approved, nearly 150,000 patients have received VNS worldwide over the past 25 years. Therefore, limited patients in the study area have received VNS, so this study expects to recruit <5 patients for this study goal.

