## **6.0 Number of Subjects**

This study will recruit 90 community individuals who meet the above inclusion and exclusion criteria, 50% of which will be female. Participants ( $n = 45$ ) who are healthy controls will be recruited to establish the dose response curve. Then this dose will be administered to 40 individuals with anxiety and trauma related symptoms. Participants with implanted VNS ( $n = 5$ ) will be recruited for similar procedures.

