After all electrodes are attached, a 1) baseline (5-10 min) physiology measurement will be taken. Then stimulation will begin. See additional information in Section 3.0 (Intervention to be Studied). Participants in the taVNS group (not having implanted VNS) will be randomized to one of 9 doses with 5 participants per dose, increasing in 10 minute increments of active stimulation. All active sessions per dose will be delivered contiguously and at the end of the stimulation period, and sham stimulation at the beginning. This is to ensure that all participants have the same lapse of time between pre- and post-stimulation recording. That is, if a participant is randomized to 60 minutes of active stimulation, the first 30 minutes would be sham stimulation.

For participants with previously implanted vagus nerve stimulation devices, stimulation will be delivered for 30 minutes. They will subsequently be invited to revisit the lab to receive non-invasive taVNS delivered in a comparable manner to the healthy subjects for 30 minutes.

Additional physiology measurements will be taken 2) concurrent with stimulation and during a final recovery measurement (5-10 mins) after stimulation has concluded.

During the base, recovery, and during 3 time points during the 90-minute stimulation period (i.e., 30 minutes, 60 minutes, and 90 minutes), a Passive Auditory Oddball Task will be administered. During this task a relaxing movie (i.e., silent sand art film) is presented concurrent with standard and deviant tones; MMN task from the ERP Compendium of Open Resources and Experiments - ERP CORE; Kappenman et al., 2020; Eriksen & Eriksen 1974).

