## 12.0 Data Management

Power: Dose-response studies are not powered in the traditional manner. To resolve the shape of the continuous dose response function, it is statistically more efficient to select more doses as opposed to more participants (O’Quigley & Conaway, 2010; Kuljus et al., 2006). The number of observations within each dose primarily accounts for sampling variability, which could be achieved with 2-3 observations. Capturing variability is essential to the planned analyses, which underweight the points of greatest variability in estimating the response curve. Thus, the sample size of  $N = 45$  was determined sufficient to accomplish Aim 1 to establish a dose-response curve. Of note, [name] is running three funded projects with these dose-response techniques in optimizing repetitive transcranial magnetic stimulation (rTMS). An additional, sample of 45 participants are included in the case of data loss and to replicate dose-response findings/assess feasibility/tolerability on participants with anxiety or trauma related disorder or symptoms.

Analyses: The psychophysiological data will be processed using standard protocols which have previously been used in this lab and in various other studies (Sege et al., 2017, 2018, Taylor et al., 2020; Grant et al., 2015), and according to published guidelines (Blumenthal et al., 2005; Boucsein et al., 2012; Gatchel et al., 1973; Keil et al., 2014).

Dose-response relationships will be assessed using the multiple comparisons procedure with modeling (MCP-Mod) approach pre- to post-stimulation changes in physiology and behavior. To determine the reliability of a dose response, MCP-Mod fits a set of pre-specified candidate dose-response curves to the data using a multiple-comparisons technique. The pre-specified dose-response curves to be tested would be Emax, logistic, and linear. Significant curves would then be used to develop inferences on optimal doses for a follow-up adaptive-dosing design, with doses more finely resolved around the probable point of maximal efficacy as determined in this project.

**Confidentiality and Quality Control:** All study personnel will complete Social-Behavioral-Educational research CITI training, and also complete in-lab training regarding data security practices. Study personnel will be trained in the IRB protocol. The investigator, and co-investigators will be available to monitor data collection to ensure quality, confidentiality, and adherence to the IRB protocol.

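### The sex balance promised across stimulation durations cannot be met exactly with 5 per group, and the plan does not say how sex enters the allocation or the analysis

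*Combined protocol and SAP*

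**What the plan says.** Section 5.0 makes the commitment: "The recruited sample will be 50% female evenly counterbalanced across active stimulation duration and sham conditions". It is the only place that links sex to duration.

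The allocation is described in three places. Section 1.0: "We will first recruit 45 healthy participants (randomized to 9 different dose durations". Section 3.0: "Participants will be randomized to one of 9 dose durations with 5 participants per dose". Section 10.0: "randomized to one of 9 doses with 5 participants per dose". None of them names strata, separate lists, blocks, minimisation or a quota by sex.

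Section 6.0 sets the overall target: "This study will recruit 90 community individuals who meet the above inclusion and exclusion criteria, 50% of which will be female". The 90 are made up of 45 healthy participants, 40 with anxiety or trauma symptoms and 5 with an implanted device.

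On sham, Section 3.0 says: "All active sessions per dose will be delivered contiguously and at the end of the stimulation period, and sham stimulation at the beginning". In the randomized cohort, sham is therefore a lead-in within the session and not a separate arm across which sex could be balanced.

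On the analysis, Section 12.0 says: "MCP-Mod fits a set of pre-specified candidate dose-response curves to the data using a multiple-comparisons technique". The curves are Emax, logistic and linear, fitted to the change from before to after stimulation. Sex does not appear in the model.

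**The concern.** The Section 5.0 sentence concerns allocation as well as recruitment, because it names duration. Read literally, it promises a balance that groups of 5 cannot have. Read sensibly, as near-even balance, it still needs an allocation method, and none is given. Recruiting about half women overall does not by itself balance sex within each duration.

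At 5 per duration, each person carries one fifth of a group mean. If the change in a physiological measure differs between women and men, and the share of women happens to rise or fall with duration in the one allocation that is realised, part of that difference enters the fitted curve. Section 3.0 uses the curve to choose the duration given to the next cohort. A further cost is in reporting: the trial could be described as counterbalanced without any stated step that made it so.

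**Working it through.** **Inputs.** Nine durations from 10 to 90 minutes and 5 per duration (Sections 3.0 and 10.0); 45 randomized (Section 1.0); 90 in total, half female (Section 6.0). A sex effect on the change score is not given, so a range is assumed in step 5.

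**1. The plan's own figures.** 9 × 5 = 45, and 45 + 40 + 5 = 90. Both reproduce.

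**2. Is an even split possible?** Half of 5 is 2.5 and half of 45 is 22.5, so no exact split exists within a duration or in the randomized cohort. Half of 90 is 45, so 50% is attainable for the total. If *a* groups have 3 women and the rest have 2, the cohort has 18 + *a* women: *a* = 4 gives 22 of 45 (48.9%) and *a* = 5 gives 23 of 45 (51.1%).

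**3. If sex were not used in the allocation.** Fix 22 women of 45 (23 gives the same results by symmetry) and count allocations exactly. The total is C(45,22) = 4,116,715,363,800.

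- A given group is single-sex: [C(40,17) + C(40,22)] / C(45,22) = 4.9%. The expected number of such groups is 9 × 0.0491 = 0.44.
- No group is single-sex: the coefficient of x²² in (5x + 10x² + 10x³ + 5x⁴)⁹ is 2,659,429,687,500. Divided by the total this is 0.646, so at least one group is single-sex in 35.4%.
- Every group at 2:3 or 3:2: C(9,4) × 10⁹ / C(45,22) = 126 × 10⁹ / 4.117 × 10¹² = 3.1%. At least one group is 4:1 or worse in the other 96.9%.
- The sex-duration correlation has mean 0 and SD 1/√44 = 0.151. By simulation it exceeds 0.2 in absolute value in about 19% of allocations and 0.3 in about 4.5%.

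**4. If Section 5.0 is carried out as 2:3 or 3:2 in every group.** No group is single-sex. What remains is where the 3-woman groups fall. Code duration as −4 to 4, so the sum of squares over 45 people is 5 × 60 = 300. The sum of squares for sex is 22 × 23 / 45 = 11.24.

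- Four 3-woman groups at the four longest durations: the cross-product is 3(1+2+3+4) + 2(0−1−2−3−4) = 30 − 20 = 10, so r = 10 / √(300 × 11.24) = 0.17.
- Alternating 3, 2, 3, 2, 3, 2, 3, 2, 3: the cross-product is 3(−4−2+0+2+4) + 2(−3−1+1+3) = 0, so r = 0. The reverse pattern also gives 0.
- Alternating cells against the curved shapes, assuming midpoints of 10 to 45 minutes and a logistic scale of 10 minutes: |r| is about 0.013 to 0.025 for Emax and 0.003 to 0.029 for logistic.

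**5. What ignoring sex does to the slope.** Assume an additive sex difference δ in the change score, in within-sex SD units, with sex used neither in the allocation nor in the model. The SD of the linear slope is multiplied by √(1 + δ² × 11.24/44) = √(1 + 0.2556 δ²).

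| δ (assumed) | Multiplier | Inflation |
|---|---|---|
| 0.3 | 1.011 | about 1% |
| 0.5 | 1.031 | about 3% |
| 0.8 | 1.079 | about 8% |

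The mean slope error over allocations is 0.

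**The case against.** The strongest reply is that Section 5.0 is itself the commitment to use sex in assigning durations. Sections 3.0 and 10.0 are silent on sex; they do not exclude it. A reader might infer from the 35% and 3% figures that the trial runs a one-in-three risk of a single-sex group. The documents do not support that: those rates describe an allocation that disregards the promise, and if the promise is followed no single-sex group arises. This stands, and the figures must carry that condition.

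It is also fair to say that 2:3 is what most readers would take near-even to mean in a group of 5, and that the 50% in Section 6.0 is attainable for the total of 90. The odd group size is therefore the lesser point.

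Finally, chance imbalance in sex is like chance imbalance in any other baseline factor. It has mean zero, and the analysis of change scores removes stable sex differences in level, so that only a difference in the change itself could matter. The documents give no size for one. This also stands, and it limits the point to a modest loss of precision.

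What the reply does not answer is that no section turns the promise into an allocation rule, that near-even cells alone still permit r = 0.17, and that the analysis makes no use of a factor the plan set out to balance.

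**Conclusion.** The point holds as a minor one. The balance in Section 5.0 is not attainable as worded for the randomized cohort, the way sex enters the allocation is not stated, and the dose-response model has no sex term.

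The likely cost is small: about 1% to 8% on the SD of the linear slope if sex is ignored throughout. This rests on an assumed additive sex difference of 0.3 to 0.8 SD in the change score, with 22 or 23 women of 45.

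A reader might go further and infer that the dose-response curve, or the duration chosen from it, would be distorted by sex. The documents do not support that. They report no sex effect on the change scores, and under random allocation the effect on the slope averages to zero. The arithmetic on group splits is certain; whether actual groups would be unbalanced depends on an allocation procedure that the documents do not describe.

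**What to change.** 1. Replace the Section 5.0 sentence with an attainable one: 2 or 3 participants of each sex per duration, giving 22 or 23 women of 45, with 50% female as the target for the total of 90. Drop or explain the reference to balancing across sham conditions.
2. State in Sections 3.0 and 10.0 that durations are allocated from separate lists for women and men, with 3:2 and 2:3 cells alternating along the nine durations. For example, 3 women and 2 men at 10, 30, 50, 70 and 90 minutes, and 2 women and 3 men at 20, 40, 60 and 80 minutes, gives 23 women and 22 men. The correlation with linear duration is zero, and it is near zero for the Emax and logistic shapes.
3. Add sex as a covariate in the dose-response model in Section 12.0. The cells remove the link between sex and duration; the covariate takes any sex difference out of the residual variance.

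The cost is a revised allocation list, a few sentences and one degree of freedom (for a model with nine duration means, from 45 − 9 = 36 to 35). The last places must also be filled by a given sex, which may slow the end of recruitment. Sample size, durations and procedures do not change.

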### ***Inclusion Criteria***

- Ages 18-65 years
- English speaking

- Healthy, Non-treatment-seeking community members who do not have a mental health diagnosis and individuals seeking treatment for an anxiety, mood, trauma-related, or obsessive-compulsive disorder.
- Treatment and non-treatment-seeking community members with anxiety, mood, trauma-related, or obsessive-compulsive disorder or symptoms.
- Patients at MUSC who have received implanted VNS for depression or stroke recovery.

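### Sex is balanced across the stimulation durations by design, but the MCP-Mod analysis described has no sex term, so the dose test may be mildly conservative

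*Combined protocol and SAP*

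**What the plan says.** Section 5.0 (Inclusion and Exclusion Criteria/ Study Population) sets a rule for sex: "The recruited sample will be 50% female evenly counterbalanced across active stimulation duration and sham conditions". Section 6.0 repeats the 50% target for all 90 participants. Section 3.0 gives the allocation for the dose-response stage: "Participants will be randomized to one of 9 dose durations with 5 participants per dose", which is 45 people.

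The analysis is one paragraph of section 12.0: "Dose-response relationships will be assessed using the multiple comparisons procedure with modeling (MCP-Mod) approach pre- to post-stimulation changes in physiology and behavior". The candidate shapes follow: "The pre-specified dose-response curves to be tested would be Emax, logistic, and linear". No factor, covariate or stratification term is named. Section 12.0 also says "Dose-response studies are not powered in the traditional manner", and it gives no standard deviation, significance level or effect size.

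**The concern.** A factor used to balance allocation normally appears in the model. Balancing removes that factor's contribution from the true sampling error of the dose comparison. If the model omits the factor, its contribution still enters the estimated residual variance. The estimate benefits from the balance, but the standard error does not show it.

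With five people per duration there are 45 − 9 = 36 error degrees of freedom, so there is little precision to spare. According to section 12.0, significant curves are to guide the choice of optimal doses, and section 3.0 sends the chosen duration on to the treatment-seeking sample. A test that is conservative for an avoidable reason makes it somewhat more likely that a real dose-response signal is missed.

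**Working it through.** **Inputs from the documents.** Nine durations with five people each; sex counterbalanced across durations; outcome is pre- to post-stimulation change. The plan's own figure reproduces: 9 × 5 = 45. There is no power calculation to reproduce.

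**Assumed inputs.** R² is the share of the variance in change due to sex, taken as 0, 5%, 10% or 20%. Residual variance is common to all durations. The test is two-sided at 0.05. Five people cannot be split equally by sex, so I take splits of 2:3 and 3:2 in alternate durations (22 of 45 female). On that layout sex has zero correlation with duration, so the estimated linear contrast is the same with or without a sex term and only its standard error changes.

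**Reading 1: R² as a population value.** Set the variance of change to 1 in a population that is half female. The variance within each sex is then 1 − R², and the male-female difference δ satisfies δ²/4 = R².

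- Sex sum of squares within one duration: 5 × 0.4 × 0.6 × δ² = 1.2δ² = 4.8R².
- Over nine durations, per error degree of freedom: 9 × 4.8R² / 36 = 1.2R².
- Expected residual variance without sex: (1 − R²) + 1.2R² = 1 + 0.2R².
- Expected residual variance with sex: 1 − R².
- Standard error ratio, with over without: √[(1 − R²)/(1 + 0.2R²)].

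**Reading 2: R² as the in-sample share of the residual sum of squares.** The ratio is √[(1 − R²) × 36/35].

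| R² (assumed) | Reading 1 | Reading 2 |
|---|---|---|
| 0 | 1.00 | √(36/35) = 1.014 |
| 5% | √(0.95/1.01) = 0.97 | √(0.95 × 36/35) = 0.99 |
| 10% | √(0.90/1.02) = 0.94 | √(0.90 × 36/35) = 0.96 |
| 20% | √(0.80/1.04) = 0.88 | √(0.80 × 36/35) = 0.91 |

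**What this does to the test.** Under reading 1 with no dose effect, the true variance of the linear contrast is proportional to 1 − R², but the unadjusted test uses about 1 + 0.2R². Its critical value of 2.028 (t, 36 df) therefore acts like 2.028 divided by the ratio: 2.09, 2.16 and 2.31 at R² of 5%, 10% and 20%. The corresponding two-sided rejection rates are about 4.4%, 3.8% and 2.7% in place of 5%. A simulation of this layout agreed, and with sex in the model the rate was about 5% throughout.

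**How large a sex effect this needs.** A male-female difference in change of g within-sex standard deviations gives R² = (g²/4)/(1 + g²/4). For g = 0.2 this is 0.01/1.01, about 1%. For g = 0.5 it is 0.0625/1.0625, about 6%. For g = 0.8 it is 0.16/1.16, about 14%. For g = 1 it is 0.25/1.25 = 20%.

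**The case against.** The strongest reply is that the benefit rests wholly on an R² that the documents do not supply. The outcome is a change score, so a stable difference between men and women in the level of a physiological measure cancels. Only an effect of sex on the change itself is left, and the 20% case needs a difference of a full within-sex standard deviation. This stands: the gain may be negligible.

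A second reply is that section 12.0 is brief and does not set out a linear predictor, so its silence is not a decision to leave sex out. This also stands, and a reader should not infer that the plan excludes sex or contradicts itself. It does not remove the point, because the analysis run as described would have no sex term.

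A reader might also put age in the same class, since the eligibility range is wide ("Ages 18-65 years"). The documents do not support that. Age is an entry limit only, and nothing balances or stratifies on it, so omitting it is not a mismatch between design and analysis. Under randomisation, chance age differences between durations do not bias the dose comparison, and their sampling variation is already in the unadjusted standard error. Adjusting for an unbalanced covariate also adds some variance of its own, so the ratios above cannot be carried over to a model with sex and age.

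**Conclusion.** The point holds for sex, as a minor one. Section 5.0 balances sex across durations and the analysis in section 12.0 has no term for it. If sex affects the change, the dose-contrast standard error is too wide and the test conservative. A reader might infer that the dose-response curve is biased; it is not, and the loss is one of stated precision only.

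Including sex multiplies the standard error by about 0.97–0.99, 0.94–0.96 or 0.88–0.91 at an assumed R² of 5%, 10% or 20%. Each range spans the population and in-sample readings of R². If R² is zero, the standard error rises by 0 to 1.4%. These figures assume a common residual variance, the R² values shown and, for the population reading, near-even sex splits within each duration. None of the R² values comes from the documents, so the real gain could be close to nil.

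**What to change.** In section 12.0, state that the change score is modelled with duration as a nine-level factor and sex as a fixed factor. State also that the generalised MCP-Mod contrasts and curve fits are applied to the sex-adjusted dose means and their covariance matrix. If sex is deliberately left out, say so and why.

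An age term is optional. If one is wanted, it should be prespecified with its own justification rather than added because sex is there.

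The cost is one sentence and one of 36 error degrees of freedom. The demographics questionnaire in section 10.0 and the sex-balanced recruitment mean that no new data should be needed.
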